# 3.1.6. Physical Examinations

Complete physical examinations will be conducted at screening or upon admission for a participant's first period in the study. At all other timepoints, a brief physical exam may be performed for the findings during a previous exam or new/open AEs at the investigators discretion. Height and weight will only be measured at the screening visit.

Physical examination findings collected during the study will be considered source record and will not be required to be reported, unless otherwise noted.

Any untoward physical examination findings that are identified during the active collection period will be captured as AEs or SAEs, if those findings meet the definition of an AE or SAE, and will be summarized as part of the standard AE outputs.

# 3.2. Secondary Endpoint(s)

Blood samples for PK analysis of PF-06954522 will be taken according to the SoA in the protocol.

The plasma PK parameters for PF-06954522, following oral dose administration, will be derived from the plasma concentration-time profiles using standard noncompartmental methods as detailed in Table 2, as data permit. Table 2 shows the analysis scale and method for each parameter.

In all cases, actual PK sampling times will be used in the derivation of PK parameters. If actual PK sampling times are not available, nominal PK sampling times will be used in the derivation of PK parameters.

The following plasma PK parameters as described in Table 2 will be determined:

Table 2. Summary of PF-06954522 plasma PK parameters to be calculated.

Parameter	Definition	Method of Determination	Analysis Scale	Analysis Method
AUC inf *	Area under the plasma concentration-time profile from time 0 extrapolated to infinite time	AUC last + (C last */k el ), where C last * is the predicted plasma concentration at the last quantifiable timepoint estimated from the log-linear regression analysis	ln	A, D
AUC last	Area under the plasma concentration-time profile from time 0 to the time of the last quantifiable concentration (C last )	Linear/Log trapezoidal method	ln	A, D
$C_{max}$	Maximum plasma concentration	Observed directly from data	ln	A, D
$T_{\text{max}}$	Time for Cmax	Observed directly from data as time of first occurrence	R	D
t 1/2 *	Terminal elimination half-life	Log e (2)/k el , where k el is the terminal phase rate constant calculated by a linear regression of the loglinear concentrationtime curve. Only those data points judged to describe the terminal log-linear decline will be used in the regression.	R	D

\*=if data permits.

Abbreviations: A=analyzed using a statistical model (if applicable); D=displayed with descriptive statistics as outlined in Table 5 in Section 6.2; ln=natural-log transformed; R = raw (untransformed).

# 3.3. Other Endpoint(s)

# 3.3.1. Additional Plasma PF-06954522 PK Parameters

Additional plasma PF-06954522 PK parameters, as described in Table 3, will be determined:

Table 3. Additional PF-06954522 Plasma PK Parameters

Parameter	Definition	Method of Determination	Analysis Scale	Analysis Method
AUC inf (dn)*	Dose-normalized AUC inf	AUC inf /Dose	ln	D
AUC last (dn)	Dose-normalized AUC last	AUC last /Dose	ln	D
C max (dn)	Dose-normalized C max	C max /Dose	ln	D
CL/F*	Apparent clearance	Dose/AUC inf	ln	D
V z /F*	Apparent volume of distribution	Dose/(AUC inf x k el )	ln	D

\*=if data permits.

Abbreviations: D=displayed with descriptive statistics as outlined in Table 6 in Section 6.3.1; dn = normalized to a 1 mg PF-06954522 dose; ln=natural-log transformed; R = raw (untransformed).

# 3.3.2. Plasma PF-06954522 PK Parameters During Food Effect Period (if conducted)

If conducted, the plasma PF-06954522 PK parameters described in Table 2 and Table 3 will also be determined during the fed period.

# 3.3.4. Safety Summaries and PK Parameters During Japanese Cohort (if conducted)

If conducted, the safety summaries as described in Section 3.1 and the PK parameters as described in Sections 3.2 and 3.3.1 will also be determined for the Japanese cohort.

#### 3.4. Baseline Variables

Not applicable.

[figure not shown]
# 3.5. Safety Endpoints

See Section 3.1 for details.

# 4. ANALYSIS SETS (POPULATIONS FOR ANALYSIS)

Data for all participants will be assessed to determine if participants meet the criteria for inclusion in each analysis population prior to unblinding and releasing the database and classifications will be documented per standard operating procedures.

Population	Description	Applicable Analysis (for additional information refer to section 6)
j j	"Enrolled" means a participant's, or their legally authorized representatives, agreement to participate in a clinical study following completion of the informed consent process and randomization to study intervention.	
Set i	All participants randomly assigned to study intervention and who take at least 1 dose of study intervention. Participants will be analyzed according to the product they actually received.	Section 6.1 Primary Endpoint(s), Section 6.3.4 Safety Summaries and PK Parameters During Japanese Cohort, 6.5.1 Baseline Summaries
Concentration Set	All participants randomly assigned to study intervention and who receive at least 1 dose of study intervention and in whom at least 1 plasma/urine concentration value is reported.	Section 6.2 Secondary Endpoint(s), 6.3.4 Safety Summaries and PK Parameters During Japanese Cohort
Set i	All participants randomly assigned to study intervention and who receive at least 1 dose of study intervention and have at least 1 of the PK parameters of interest calculated.	Section 6.2 Secondary Endpoint(s), Section 6.3.1 Additional Plasma PF- 06954522 PK Parameters, Section 6.3.2 Plasma PF- 06954522 PK Parameters During Food Effect Period, Section 6.3.4 Safety Summaries and PK Parameters During Japanese Cohort

#### 5. GENERAL METHODOLOGY AND CONVENTIONS

## 5.1. Hypotheses and Decision Rules

There is no statistical hypothesis testing planned for this study, and no statistical decision rules will be applied.

#### 5.2. General Methods

Unless otherwise stated, all summaries and plots will be presented by dose level, with data from different populations (e.g. non-Japanese and Japanese participants), if appropriate, reported separately. Each dietary allocation (i.e., standard and high fat breakfast) will also be reported separately.

If a dose level is repeated across 2 or more cohorts (within a dietary allocation), the data will be combined.

Unless otherwise stated the summary tables and/or statistical analyses may only include a single pooled placebo group across all included cohorts. Placebo will be pooled from all dose escalation periods but not the fed period or the Japanese cohort.

#### 5.2.1. Analyses for Continuous Endpoints

Unless otherwise stated, continuous variables will be presented using summary statistics: number of observations, arithmetic mean, standard deviation, median, minimum and maximum values.

Log transformed continuous variables will be presented using summary statistics: number of observations, arithmetic mean, median, CV%, standard deviation, minimum, maximum, geometric mean and geometric CV%.

#### 5.2.2. Analyses for Categorical Endpoints

Categorical variables will be presented using summary statistics: number of observations and percentages.

#### 5.2.3. Mixed Effects Model

A mixed effects model with treatment as a fixed effect and participant as a random effect will be used.

Estimates of the adjusted (least squares) mean differences (Test-Reference) and corresponding 90% confidence intervals will be obtained from the model. The adjusted mean differences and 90% confidence intervals for the differences will be exponentiated to provide estimates of the ratio of adjusted geometric means (Test/Reference) and 90% confidence intervals for the ratios.

The mixed effects model will be implemented using SAS Proc Mixed, with REML estimation method and the Kenward-Roger degrees of freedom algorithm.

Residuals from the models will be examined for normality and the presence of outliers via visual inspection of plots of residuals vs predicted values and normal probability plots of residuals, but these will not be included in the clinical study report. If there are major deviations from normality or outliers (where studentized [conditional] residuals are greater than 3 or less than -3), then the effect of these on the conclusions may be investigated through alternative transformations and/or analyses excluding outliers. Justification for any alternative to the planned analysis will be given in the report of the study if applicable.

Example code is shown in Appendix 1.

# 5.3. Methods to Manage Missing Data

For the analysis of safety endpoints, the sponsor data standard rules for imputation will be applied.

# 5.3.1. Concentrations Below the Limit of Quantification

In all PK data presentations (except listings), concentrations below the limit of quantification (BLQ) will be set to zero. In listings BLQ values will be reported as "<LLOQ", where LLOQ will be replaced with the value for the LLOQ.

In all exploratory biomarker (CCI) data presentations (except listings), concentrations below the limit of quantification (BLQ) will be set to the lower limit of quantification (LLQQ).

# 5.3.2. Deviations, Missing Concentrations and Anomalous Values

In PK and exploratory biomarker summary tables and plots of median profiles, statistics will be calculated having set concentrations to missing if one of the following cases is true:

- 1. A concentration has been collected as ND (ie, not done) or NS (ie, no sample),
- 2. A deviation in sampling time is of sufficient concern or a concentration has been flagged anomalous by the pharmacokineticist/statistician.

Note that summary statistics will not be presented at a particular time point if more than 50% of the data are missing.

Participants who experience events that may affect their PK profile (e.g., lack of compliance with dosing or vomiting) may be excluded from the PK analysis. At the discretion of the pharmacokineticist, a concentration value may also be excluded if the deviation in sampling time is of sufficient concern or if the concentration is anomalous for any other reason.

A full list of protocol deviations will be compiled and reviewed to identify major and minor deviations prior to database closure.

#### 5.3.3. Plasma Pharmacokinetic Parameters

Actual PK sampling times will be used in the derivation of plasma PK parameters.

If a PK parameter cannot be derived from a participant's concentration data, the parameter will be coded as NC (i.e., not calculated). (Note that NC values will not be generated beyond the day that a participant discontinues.)

In summary tables, statistics will be calculated by setting NC values to missing; and statistics will be presented for a particular treatment group/analyte with ≥3 evaluable measurements. For statistical analyses (i.e., mixed effects model), PK parameters coded as NC will also be set to missing; and analyses will not be performed for a particular parameter if more than 50% of the data are NC.

If an individual participant has a known biased estimate of a plasma PK parameter (due, for example, to an unexpected event such as vomiting before all the compound is adequately absorbed in the body), this will be footnoted in summary tables and may not be included in the calculation of summary statistics or statistical analyses.

#### 6. ANALYSES AND SUMMARIES

For all presentations, study day will refer to the day within a particular treatment period, unless otherwise specified.

**NOTE:** For all analyses presented below 'by treatment' refers to by dose, population (if applicable) and dietary allocation (if applicable), as described in Section 5.2, unless otherwise stated. Overall by population refers to reporting Japanese and Non-Japanese populations separately (i.e. Cohort 1 and Cohort 2 together, and Cohort 3 separately).

# 6.1. Primary Endpoint(s)

#### 6.1.1. Adverse Events

AEs will be listed and summarized by treatment and overall by population and in accordance with sponsor reporting standards using the safety population defined in Section 4.

Incidence and severity of TEAE tables will additionally be produced ('All causality' and 'Treatment related,' separately) to summarize the total number of adverse events by preferred term, which will be reported by treatment and overall by population, in accordance with sponsor reporting standards using the safety analysis set defined in Section 4.

The AEs will be presented sorted in descending frequency based on the overall number of AEs (by preferred term or system order class as appropriate) across doses.

#### 6.1.2. Clinical Safety Laboratory Data

Safety laboratory data will be listed and summarized by treatment and overall by population, in accordance with the sponsor reporting standards using the safety analysis set defined in Section 4. Baseline is as defined in Section 3.1.2.

Data collected at screening that are used for inclusion/exclusion criteria, will be considered source data, and will not be required to be reported, unless otherwise noted.

In summary and listing tables, laboratory abnormalities occurring pre-dose on Day -1 for each period starting with Period 2 (or a participant's individual second dosing Period, for any participant that starts the study after Period 1), will be attributed to the dose from the previous period (e.g., for Cohort 1, an occurrence pre-dose at Period 2 Day -1 will be attributed to the Period 1 dose). Any abnormality pre-dose in Period 1 or pre-dose at a participant's first dosing period would be reported as that participant's baseline measure for the period. Unplanned assessments will be included in summary abnormality tables and listings.

# 6.1.3. Vital Signs

Absolute values and changes from baseline (as defined in Section 3.1.3) in supine systolic and diastolic blood pressure, respiratory rate, temperature, and pulse rate will be listed, and summarized by treatment and timepoint, according to sponsor reporting standards using the safety population defined in Section 4.

Mean absolute values and mean changes from baseline for systolic and diastolic blood pressure, respiratory rate, temperature, and pulse rate will be plotted against time point. On each plot, there will be 1 line for each treatment with all doses on the same plot. Corresponding individual plots of changes from baseline will also be produced for each treatment.

Maximum and minimum absolute values and changes from baseline (as defined in Section 3.1) for supine vital signs will also be summarized descriptively by treatment using categories as defined in Appendix 2.

Numbers and percentages of participants meeting the categorical criteria will be provided. All planned and unplanned post dose time points will be counted in these categorical summaries. All values meeting the criteria of potential clinical concern will be listed.

Values meeting the categorical criteria occurring pre-dose on Day 1 for each period starting with Period 2, will be attributed to the dose from the previous period (e.g., for cohort 1, an occurrence pre-dose at Period 2 Day 1 will be attributed to the Period 1 dose). For any participant who starts the study after Period 1, the same considerations as described in Section 6.1.2 apply.

Data collected at screening that are used for inclusion/exclusion criteria, will be considered source data, and will not be required to be reported, unless otherwise noted. Unplanned assessment will be listed but will be excluded from safety summary except for categorical summaries.

# 6.1.4. Continuous Cardiac Monitoring

Continuous cardiac monitoring will be performed using telemetry as outlined in the protocol. Data will be reviewed and summarized on an ongoing basis during the study to evaluate the safety of participants.

All abnormal rhythms will be recorded and reviewed by the investigator for the presence of rhythms of potential clinical concern. The time, duration, and description of the clinically significant event will be recorded in the CRF. Events deemed of clinical concern will be recorded as AEs and will be summarized as part of the standard AE outputs.

# 6.1.5. Electrocardiograms

Absolute values and changes from baseline in QT, heart rate, QTcF, PR and QRS will be summarized by treatment and timepoint using sponsor reporting standards, using the safety analysis set defined in Section 4. Baseline is as defined in Section 3.1.5.

Mean changes from baseline in QT, heart rate and QTcF will be plotted against time post-dose. On each plot there will be one line for each treatment. Corresponding individual plots of changes from baseline will also be produced for each treatment.

Changes from baseline in QTcF will also be plotted separately against drug concentrations of PF-06954522. This will be a scatter plot for all observations where QTcF and drug concentration are recorded. Placebo data will also be included (with drug concentration set to zero). Different symbols will be used for each treatment.

Maximum increase from baseline for QTcF, heart rate, PR and QRS values will be summarized by treatment according to sponsor reporting standards.

ECG endpoints and changes from baseline (QTcF [1], PR and QRS) will also be summarized descriptively by treatment (if applicable) using categories as defined in Appendix 2. Numbers and percentages of participants meeting the categorical criteria will be provided. All planned and unplanned postdose time points will be counted in these categorical summaries.

Values meeting the categorical criteria occurring pre-dose on Day 1 for each period starting with Period 2, will be attributed to the treatment from the previous period (e.g., for cohort 1, an occurrence pre-dose at Period 2 Day 1 will be attributed to the Period 1 dose). For any participant who starts the study after Period 1, the same considerations as described in Section 6.1.2 apply.

Listings of participants with any single post-dose value >500msec will also be produced for QTcF.

Data collected at screening that are used for inclusion/exclusion criteria, will be considered source data, and will not be required to be reported, unless otherwise noted. Unplanned assessment will be listed but will be excluded from safety summary except for categorical summaries.

In addition, an attempt will be made to explore and characterize the relationship between plasma concentration and QT interval length using a PK/PD modeling approach. If a PK/PD relationship is found, the impact of participant factors (covariates) on the relationship will be examined. The results of such analyses may not be included in the CSR.

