8.3.3. Electrocardiograms

Standard 12-lead ECGs will be collected at times specified in the SoA section of this protocol using an ECG system that automatically calculates the HR and measures PR, QT, QTcF, and QRS intervals. All scheduled ECGs should be performed after the participant has rested quietly for at least 5 minutes in a supine position.

Triplicate 12-lead ECGs will be obtained approximately 2 to 4 minutes apart; the average of the triplicate ECG measurements collected at -1.0, -0.5, and 0 hours pre-dose on Day 1 of each period will serve as each participant's baseline QTcF value.

To ensure safety of the participants, a qualified individual at the investigator site will make comparisons to baseline measurements. Additional ECG monitoring will occur if a) the mean value from the triplicate measurements for any postdose QTcF interval is increased by ≥60 ms from the baseline and is >450 ms; or b) an absolute QT value is ≥500 ms for any scheduled ECG. If either of these conditions occurs, then a single ECG measurement must be repeated at least hourly until QTcF values from 2 successive ECGs fall below the threshold value that triggered the repeat measurement.

For single ECG collection, additional ECG monitoring will occur if a) a postdose QTcF interval is increased by ≥60 ms from the baseline **and** is >450 ms; or b) an absolute QT value is ≥500 ms for any scheduled ECG. If either of these conditions occurs, then 2 additional ECGs will be collected approximately 2 to 4 minutes apart to confirm the original measurement. If the QTcF values from these repeated ECGs remain above the threshold value, then a single ECG must be repeated at least hourly until QTc values from 2 successive ECGs fall below the threshold value that triggered the repeat measurement.

If a) a postdose QTcF interval remains ≥ 60 ms from the baseline and is ≥ 450 ms; or b) an absolute QT value is ≥ 500 ms for any scheduled ECG for greater than 4 hours (or sooner, at the discretion of the investigator); or c) QTcF value get progressively longer, the participant should undergo continuous ECG monitoring. A cardiologist should be consulted if QTcF values do not return to less than the criteria listed above after 8 hours of monitoring (or sooner, at the discretion of the investigator).

In some cases, it may be appropriate to repeat abnormal ECGs to rule out improper lead placement as contributing to the ECG abnormality. It is important that leads be placed in the

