9.3.1.1. Electrocardiogram Analyses

Changes from baseline for the ECG parameters HR, QT interval, QTcF, PR interval, and QRS complex will be summarized by treatment and time. The frequency of uncorrected QT values above 500 ms will be tabulated.

The number (%) of participants with maximum post-dose QTcF values and maximum increases from baseline in the following categories will be tabulated by treatment:

Safety QTcF Assessment

egree of Prolongation Mild (ms) Moderate (ms) Severe (ms)	Moderate (ms) Severe (ms)	Mild (ms)	Degree of Prolongation
---	---------------------------	-----------	------------------------

Absolute value	>450-480	>480-500	>500
Increase from baseline		30-60	>60

If more than 1 ECG is collected at a nominal time after dose administration (for example, triplicate ECGs), the mean of the replicate measurements will be used to represent a single observation at that time point. If any of the 3 individual ECG tracings has a QTcF value >500 ms, but the mean of the triplicates is not >500 ms, the data from the participant's individual tracing will be described in a safety section of the CSR in order to place the >500 ms value in appropriate clinical context. However, values from individual tracings within triplicate measurements that are >500 ms will not be included in the categorical analysis unless the average from the triplicate measurements is also >500 ms. Changes from baseline will be defined as the change between the postdose QTcF value and the average of the pre-dose triplicate values at -1, -0.5, and 0 hours pre-dose on Day 1.

In addition, an attempt will be made to explore and characterize the relationship between plasma concentration and QT interval length using a PK/PD modeling approach. If a PK/PD relationship is found, the impact of participant factors (covariates) on the relationship will be examined. The results of such analyses may not be included in the CSR.

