## 3.1.5. Electrocardiograms

A single 12-lead ECG will be obtained on all participants at screening, follow-up visit and at early termination (if applicable). 12-lead ECGs will be recorded in triplicate at all other times as detailed in the SoA in the protocol. The average of the triplicate readings collected at each assessment time will be calculated for each ECG parameter. If one or two of the triplicates are missing, the non-missing values will be used for the average, and missing values will not be imputed.

If any of the 3 individual ECG tracings has a QTcF value >500 msec, but the mean of the triplicates is not >500 msec, the data from the participant's individual tracing will be described in a safety section of the CSR in order to place the >500- msec value in appropriate clinical context. However, values from individual tracings within triplicate measurements that are >500 msec will not be included in the categorical analysis unless the average from the triplicate measurements is also >500 msec.

The average of the triplicate ECG measurements over the 3 pre-dose measurement times (-1H, -0.5H, and pre-dose 0H; total of 9 ECG measurements) collected before morning dose administration on Day 1 will serve as each participant's baseline value in each study period.

ECG endpoints include heart rate, QT interval, PR interval and QTcF and QRS complex. If not supplied QTcF will be derived using Fridericia's heart rate correction formula [1]:

QTcF (msec) = QT (msec) / (RR)1/3 where RR (sec) = 60/HR (if RR not provided).

The following endpoints will be determined:

• Change from baseline in QT, QTcF, PR, QRS interval and heart rate

- The maximum post-dose QTcF, heart rate, PR and QRS interval
- The maximum increase from baseline over all measurements taken post-dose for QTcF, heart rate, PR and QRS values

The maximum increase from baseline will be calculated by selecting the maximum change from baseline over the respective period, except in the case where a participant does not show an increase. In such an instance, the minimum decrease should be taken.

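### SAP 3.1.5 takes the maximum ECG increase over every post-dose reading, but SAP 6.1.5 read literally leaves unplanned ECGs out of its summary, so the maximum can be too low and can disagree with the categorical table

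*SAP*

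**What the plan says.** **Definition.** SAP 3.1.5 lists as an endpoint: "The maximum increase from baseline over all measurements taken post-dose for QTcF, heart rate, PR and QRS values". It sets no limit to planned time points.

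**Summary.** SAP 6.1.5 gives this endpoint its own sentence: "Maximum increase from baseline for QTcF, heart rate, PR and QRS values will be summarized by treatment according to sponsor reporting standards". The categorical tables follow as a further presentation, for QTcF, PR and QRS only.

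**Unplanned readings.** For the categorical tables, SAP 6.1.5 says: "All planned and unplanned postdose time points will be counted in these categorical summaries". Its general rule is: "Unplanned assessment will be listed but will be excluded from safety summary except for categorical summaries".

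**Source of unplanned ECGs.** Protocol 8.3.3 calls for additional monitoring in two situations. In the first, the triplicate mean "for any postdose QTcF interval is increased by ≥60 ms from the baseline" and QTcF is also above 450 ms. The second is that "an absolute QT value is ≥500 ms for any scheduled ECG". In either case "then a single ECG measurement must be repeated at least hourly until QTcF values from 2 successive ECGs fall below the threshold value" that triggered them. Protocol 8.3 also allows unscheduled safety measurements at any time.

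**The protocol's table.** Protocol 9.3.1.1 builds its categories on the same per-participant maxima: "The number (%) of participants with maximum post-dose QTcF values and maximum increases from baseline in the following categories will be tabulated by treatment".

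**The concern.** One quantity is presented twice under two rules. The categorical table counts unplanned ECGs. The maximum-increase summary, read literally, does not, although its definition includes them. Leaving readings out of a maximum can only lower it or leave it unchanged, so any error is downward. Unplanned ECGs are also not a random sample: they follow a large QTcF rise, a long QT or a perceived safety issue.

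ECG parameters are part of the primary safety endpoint, and Protocol 2.3.1 names increased heart rate as a potential risk. Heart rate is in the maximum-increase summary but has no ECG category in SAP Appendix 2, so the exception for categorical summaries does not bring an unplanned heart-rate peak back in. Excluding unplanned readings is sensible for means by nominal time. It does not fit a maximum defined over everything measured.

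**Working it through.** The plan gives no figure to reproduce. The check compares the two rules, first by reasoning, then on illustrative records, then in a small simulation.

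**1. Is the maximum-increase summary a categorical one?** No. It includes heart rate, for which SAP Appendix 2 has no ECG category, and the categorical tables are introduced separately. The exception therefore does not cover it.

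**2. The two rules.** For one participant in one period, let P be the highest planned increase and U the highest unplanned increase.
- SAP 3.1.5: maximum = max(P, U).
- SAP 6.1.5, literal: summarized value = P.
- Shortfall = max(0, U − P), which is zero unless U exceeds every planned reading.

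**3. When can the tables disagree on QTcF increase?** The Appendix 2 classes are >30 to ≤60 ms and >60 ms.
- *After the 60 ms trigger:* the triggering ECG is planned, so P ≥ 60 ms. If P > 60, both rules give the top class. Disagreement needs P exactly 60 and U > 60.
- *After the QT ≥500 ms trigger:* P can be well under 60 ms, because QTcF = QT/(60/HR)^(1/3). At QT 500 ms, a rate of 50 bpm gives 500/1.2^(1/3) = 470.5 ms, and 45 bpm gives 500/1.333^(1/3) = 454.3 ms.
- *After an ad hoc ECG:* no threshold on P applies. Planned post-dose ECGs are at 0.5, 1, 2, 3, 4, 6, 8, 10, 24, 36, 48 and 72 h (Protocol Tables 1 and 2), so every ECG between 10 and 24 h is unplanned.

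**4. Illustrative QTcF records (invented values, ms).**

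| Situation | P | Unplanned | Summarized (literal) | Defined (3.1.5) | Class differs? |
|---|---|---|---|---|---|
| 60 ms trigger, repeats lower | 63 | 58, 52, 48 | 63 | 63 | No |
| 60 ms trigger, repeat higher | 61 | 72 | 61 | 72 | No |
| 60 ms trigger, P exactly 60 | 60 | 66 | 60 | 66 | Yes |
| QT trigger or ad hoc ECG | 26 | 35 | 26 | 35 | Yes |
| Ad hoc ECG | 57 | 64 | 57 | 64 | Yes |

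For heart rate, a planned maximum of +18 bpm and an ad hoc reading of +32 bpm gives 18 summarized against 32 defined.

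With about 8 active participants per period in Cohort 1, one such record lowers the group mean by (72 − 61)/8 = 1.4 ms or (32 − 18)/8 = 1.75 bpm. If that participant has the highest value in the group, the reported group maximum is also too low, by up to 11 ms or 14 bpm.

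**5. How often does a triggered repeat exceed the planned maximum?** The documents give no QTcF variability, so the inputs are assumptions: single-tracing SD 4, 7 or 10 ms; true peak increase 50, 60 or 70 ms at 1, 3 or 5 h; 6 h decay half-life; QTcF above 450 ms. Planned values were triplicate means at the 12 times above. Hourly single repeats followed a planned increase ≥60 ms until two in a row were below 60 ms. Each setting had 4,000 simulated participants, and settings with at least 50 triggered participants were read.
- A repeat exceeded the planned maximum in 2% to 41% of triggered participants.
- Where it did, the mean excess was about 2 to 9 ms.
- The planned maximum stood in the other 59% to 98%.
- The QTcF increase class never differed, as step 3 predicts.

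The simulation does not cover the QT trigger or ad hoc ECGs.

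**6. Do vital signs have the same problem?** SAP 6.1.3 carries the same exclusion sentence, but it summarizes maxima through the Appendix 2 categories, which count unplanned values. The conflict is specific to the ECG maximum-increase summary.

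**The case against.** The strongest case for leaving the text alone has four parts.

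- **Comparability.** Planned values are triplicate means on a common schedule, while triggered repeats are single tracings in selected participants. Adding noisier readings only for them raises their maximum even without a further true rise. The documents guard against single-tracing noise elsewhere: one tracing above 500 ms within a triplicate does not count in the categories unless the mean does. This stands as a reason to flag such maxima, or to choose a planned-only definition openly. It does not reconcile 3.1.5 with 6.1.5.
- **No signal is lost.** Unplanned ECGs are listed, participants with any single post-dose QTcF above 500 ms are listed separately, and new clinically relevant ECG findings are reported as AEs. Pulse rate from vital signs has its own categories (<40 and >120 bpm), which count unplanned values. All of this stands and keeps the point small.
- **Undefined terms.** The exclusion does not define a safety summary, and the sponsor reporting standards that govern the table are not in the documents. The specific definition in 3.1.5 might be meant to prevail over a general closing sentence. That is possible, but nothing in the SAP says so, and a programmer would have to guess.
- **No decision depends on it.** The study has no hypothesis test or statistical decision rule, and nothing ties dose escalation to this table. This stands.

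A reader might also infer that the maximum is too low in every participant whose ECG triggers repeats, or that the repeats are the readings most likely to hold the true maximum. The documents support neither. The triggering ECG is planned and stays in the summary, and the repeats come after it and continue until values fall.

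**Conclusion.** The inconsistency is real and minor. Followed literally, SAP 6.1.5 summarizes a quantity that differs from the one SAP 3.1.5 defines. The summarized maximum can be too low when an unplanned reading is the participant's highest, it cannot be too high, and it can disagree with the categorical table.

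For QTcF increase, disagreement arises mainly after the uncorrected QT trigger or an ad hoc ECG. After the 60 ms trigger it needs a planned maximum of exactly 60 ms. For heart rate, an unplanned ECG peak would be listed but would enter no ECG summary table.

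The size depends on how many unplanned ECGs are taken and on within-participant variability, neither of which the documents give. With no unplanned ECGs there is no effect. The 2% to 41% range applies only to participants who meet the 60 ms trigger and rests on the assumed SDs, peaks and decay. The conclusion also assumes that the sponsor reporting standards do not already settle the matter. It would be too strong to say that the safety conclusions of the study are biased, since only one descriptive table is affected and the readings remain visible in listings.

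**What to change.** In SAP 6.1.5, limit the exclusion of unplanned assessments to the by-timepoint summaries and the mean plots. Add one sentence: maximum increase from baseline in QTcF, heart rate, PR and QRS is taken over all planned and unplanned post-dose ECGs, as Section 3.1.5 defines, and a maximum that comes from a single unplanned tracing is flagged. The maximum-increase summary and the categorical table then rest on the same readings.

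The cost is one SAP sentence and a programming flag. The downside is that single tracings are noisier than triplicate means; the flag lets a reader see which maxima depend on one.

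An alternative is to redefine the endpoint in 3.1.5 as planned time points only and footnote the difference from the categorical table. That also removes the contradiction, but an unplanned ECG heart-rate peak would still appear in listings only. Either choice is best written into the SAP before unblinded data are reviewed, since the study is sponsor-open.
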